## **STATEMENT OF COMPLIANCE**

The study will be conducted in accordance with the International Conference on Harmonisation guidelines for Good Clinical Practice (ICH E6), the Code of Federal Regulations on the Protection of Human Subjects (45 CFR Part 46), and the PCORI Clinical Terms of Award. All personnel involved in the conduct of this study have completed human subjects protection training.

[figure not shown]
Title:	Treatment Alternatives in Adult Rare Disease; Assessment of Options in Idiopathic Subglottic Stenosis
Précis:	The proposed study intends to create an international, multi-institutional prospective cohort of iSGS patients. It will enable rigorous treatment strategy comparisons to determine how well the most commonly used treatments in iSGS “work”; and what quality of life trade-offs are associated with each approach.
Objectives:	
Prospective rigorous treatment comparisons to provide the critical information to patients to allow them to answer the questions,
 

1) “given my personal characteristics, conditions and preferences, what should I expect will happen to me?” and

2) “what are my options and what are the potential benefits and harms of these options?”

 
Primary Endpoint: Treatment effectiveness: time to recurrent procedure and need for tracheostomy.
 
Secondary Endpoint: Health and quality of life tradeoffs: patient reported outcome measures in voice, swallowing, breathing, and global quality of life

Population:	All clinically confirmed iSGS patients at the participating institutions are eligible for enrolment.
Number of Sites:	45 Sites
Study Duration:	60 months
Subject Participation Duration:	>6months
Estimated Time to Complete Enrollment:	24 months

## 1.0 Background

Idiopathic subglottic stenosis (iSGS) is a rare disease in which the trachea narrows for no known reason. Although uncommon (with an estimated incidence of 1:400,000 persons per year), it is life-threatening and life-altering when severe. Both the disease and its therapies profoundly affect patients' ability to breathe, communicate and swallow. Breathing difficulties (i.e. dyspnea) is the hallmark symptom and the primary cause of death and disability. However, patients can also experience debilitating voice changes and swallowing problems due to this condition (Figure 1) or its treatment.

[figure not shown]
People with this disease often require several surgeries per year. A variety of treatments have been advanced to manage this condition but are generally categorized into: 1) endoscopic dilation of the tracheal stenosis (accomplished with rigid instruments or inflatable balloons); 2) endoscopic resection of the stenosis (often followed by prolonged medical therapy after surgery); or 3) open neck surgery with resection of the affected tracheal segment with end-to-end anastomosis (Figure 2). Each patient can require repeated surgeries to keep their trachea open, which increases the odds of treatment side effects and complications. All approaches have unique and often disabling associated side effects, which can significantly affect the patient's quality of life. However, comparative data on trade-offs have never been systematically

patients to find good information so that they can make a decision, particularly difficult because most patients present with severe symptoms, limiting their ability to explore options (as would be the case with a healthy trachea). Additionally, there is a general lack of high-quality, comparative data to aid in decision-making. Imperfect information and limited resources often lead to suboptimal decision-making as they try to balance survival, symptom relief, and quality of life considerations. In the absence of a clear standard of care, patients with a new diagnosis of iSGS face a limited number of therapeutic options, but are unable to explore them because it is urgent that they quickly relieve their breathing difficulty.

The proposed prospective study (NoAAC PR-02) is designed to fill this void, and leverages and builds upon our previous retrospective multi-institutional investigation, the North American Airway Collaborative RP-01 (NoAAC RP-01). In that study nearly 500 iSGS patients were identified and followed from ten expert tertiary care centers. Specifically, the need for repeat surgery, frequency of disease recurrence, and need for tracheostomy were identified as primary outcome measures.

Collaboration of experienced high volume centers in both the United States and the United Kingdom provided us with the largest and most representative signature of this disease’s epidemiology, natural history, and current management. Inclusion of patients across region and national borders ensured a racially/ethnically representative cohort spanning a range that includes socioeconomic disadvantaged and medically underserved patients. Interestingly, this condition was shown to be quite similar at the separate centers; as it nearly universally affects 40 – 60 year old women (median age 50.3, 95% CI 49.1 – 51.5) who undergo a median 1.75 surgeries per year (95% CI 0.8 – 2.6) (Figure 3). The NoAAC RP-01 study also found variation in the standard of care for iSGS at expert centers. Three basic treatment approaches were used (i.e. endoscopic dilation, endoscopic resection with adjuvant medical therapy, and open anterior neck surgery) despite an absence of randomized controlled trials (RCTs) or other rigorous comparative studies to assess their differential effectiveness at avoiding disease recurrence or tracheostomy.

**Figure 3.** Recurrent nature of interventions in iSGS. Operative procedure number vs. recurrence interval. Each line represents individual patient.

In contrast to the retrospective nature of RP-01, our proposed PR-02 prospective study design will directly compare effectiveness of contemporary treatments and assess their associated quality of life tradeoffs in iSGS patients. While evaluating treatment effectiveness is important, it is equally critical that the patient experience with the disease itself and its treatment be systematically characterized. This is imperative since patient and physician perspectives are often significantly discordant. To this end, NoAAC PR-02 will collect patient-reported outcomes (PROs) in the cohort at initial presentation and at *a priori* determined intervals thereafter, (e.g. immediately pre-intervention, as well as 3, 6, and 12 months post-intervention) and conduct patient interviews and focus groups (labeled “engagement studios”) to better understand the patient experience with this condition.

Beyond the gaps in understanding of the relative effectiveness of clinical outcomes, no studies have explored health-related quality of life (HRQOL) or functional outcomes in iSGS. These endpoints are important to patients and are arguably a primary determinant in decision-making. For example, results show that endoscopic dilation is associated with a higher rate of disease recurrence and thus need for repeated surgery. Meanwhile, open cricotracheal resection is a major surgery with significant immediate perioperative risks and has been associated with alterations in voice and swallowing. Open surgery appears to reduce the risk of disease recurrence, but the degree of benefit, and the trade-offs associated with this invasive surgery are questions that demand prospective study.

## 2.0 Rationale and Specific Aims

Data from our prior retrospective multi-center study highlighted potential differential treatment effects based on reduced need for repeated surgery, while also providing insight into the typical disease course for iSGS patients. However, the need to systematically validate and expand upon these findings to provide patient-centered outcomes data requires longer-term prospective study. The proposed 5-year study will evaluate clinical outcomes data and generate novel information for iSGS patients beyond the currently available center-specific treatment outcome estimates to better guide clinicians and patients and they discuss treatment options.

*In summary, the proposed study will address the questions outlined above through 3 specific aims:*

*AIM I: We will build an international, multi-center prospective cohort of iSGS patients*

*AIM II: We will prospectively compare treatments in iSGS at multiple national and international centers to determine what “works” with respect to treatment outcomes of disease recurrence and tracheostomy.*

*AIM III: We will define the trade-offs in breathing, voice, swallowing and global quality of life between each treatment approach*

## 3.0 Inclusion/Exclusion Criteria

### **Inclusion Criteria:**

- >18 years of age.
- The lesion must involve the subglottis.

### **Exclusion Criteria**

- <18years of age
- Patients without capacity to consent for themselves
- History of significant laryngotracheal traumatic injury.
- History of endotracheal intubation or tracheotomy within 2 years of presentation.
- Major anterior neck surgery.
- History of neck irradiation.
- History of caustic or thermal injuries to the laryngotracheal complex.
- History of a clinically diagnosed vasculitis or collagen vascular disease.
- Positive antinuclear cytoplasmic antibody titers.

## 4.0 Randomization

There is no randomization as part of this study. This is a prospective observational multicenter study consisting of approximately 30 centers (Appendix 1). Each center enrolling patients will utilize a common diagnostic algorithm (Appendix 2), and then apply their explicitly defined standard of care. The patients will be prospectively tracked for outcomes with respect to disease recurrence, need for

additional surgery, tracheostomy, as well as subjective patient reported outcomes in breathing, voice, and swallowing.

## 5.0 Study Procedures

**Recruitment and Enrollment:** We anticipate a sample size of 800-1100 patients recruited across the participating centers. The target goal for Vanderbilt recruitment is 750-800 patients. There are currently 40 confirmed participating sites that will contribute patients (additional centers may be added in protocol amendments provided they meet defined study site selection criteria). Participating centers include those across all regions of the U.S. and international sites in the UK. Many are academic centers that are tertiary referral centers for adult laryngotracheal stenosis (LTS) and thus have significant experience treating this rare condition. Nearly all LTS patients are ultimately referred for care and cluster at such high-volume centers, and thus we anticipate enrolling a representative patient cohort. Each research site has appropriate technological infrastructure for data collection and pathologic specimen tracking.

Study participants will be recruited via several mechanisms. Direct recruitment by participating clinician providers that diagnose and treat these patients will occur at each of the participating centers. It is expected that the majority of patients will be recruited through this approach. Patients will be identified by PI, Sub-I or Key study personnel and approached by a member of the research team at each institution regarding the study, or contacted by phone or email about the study. Participants may also be seen due to referrals in to participating sites/providers.

Additionally interested stakeholders can identify this study directly through its registration with ClinicalTrials.gov, the National Organization for Rare Disorders (NORD) website and rare disease database. Once recruited patients will undergo detailed discussion regarding risks and benefits of the trial, and informed consent will be obtained.

**Consent:** Informed consent is a process that is initiated prior to the individual agreeing to participate in the study and continues throughout study participation. Extensive discussion of risks and possible benefits of study participation will be provided to participants and their families, if applicable. A consent form describing in detail the study procedures and risks will be given to the participant, or reviewed with the patient by phone or email (i.e., econsent). Consent forms will be IRB-approved, and the participant will read and review the document or have the document read to him or her. The participant will sign the informed consent document prior to any study-related assessments or procedures, or agree to participation if consent is done by phone or email (i.e., econsent). Participants will be given the opportunity to discuss the study or think about it prior to agreeing to participate. They may withdraw consent at any time throughout the course of the study. A copy of the signed informed consent document will be given to participants for their records, i.e. by mail, email, electronic link or in person. The rights and welfare of the participants will be protected by emphasizing to them that the quality of their clinical care will not be adversely affected if they decline to participate in this study. The consent process will be documented in the clinical or research record.

Given the observational nature of the study and the minimal risk involved to patients, we will utilize established methodology for electronic consent and phone consent as alternative options to consents obtained in providers offices. Electronic consenting of patients requires an alteration of the traditional consent model to fit within electronic delivery through email or for electronic capture of consent in a face to face encounter with participants. Retention of many elements of the traditional consent procedure to ensure participant protections are in place, and we will abide by the institutional guidelines regarding these alternative consent methods. (Appendix 4).

The investigator or designee will also be available to explain the research study to the participant and answer any additional questions that may arise. After informed consent, the patient will be considered to be a participant in the study.

**Protocol.** Once enrolled and consented, patients will receive standard of care treatment at the respective center (Appendix 1) and will be followed longitudinally for symptom changes, need for further treatment, complications, and will have PROs (Appendix 2) administered at *a priori* determined intervals.

**Data collection:** *Data collection for the proposed clinical cohort study will include the following case report forms (CRFs) (Appendix 3), implemented in an electronic data capture (EDC) system (please see further details, below, regarding EDC development and implementation).*

- Baseline. Baseline data will include such things as demographics, medical and surgical history, physical exam findings, and relevant diagnostics
- Procedure. Details of initial surgical procedure will be captured (e.g. site and degree of narrowing within the trachea). This information along with other procedure related information will be abstracted from the operative procedure note and clinical record into the EDC.
- Recurrence. At patient recurrence, information regarding the date of recurrence will be captured as for the initial procedure.
- Patient-reported outcomes (PROs). Validated PRO instruments will be utilized to assess patient quality of life. These relate to voice (VHI-10), dysphagia (EAT-10), breathing (COPD dyspnea), and general quality of life (SF-12). Additionally 4 “Non-traditional” PROs focused on 1) social support, participatory decision-making style, disease anxiety and burden and fear of disease recurrence will also be administered at the initial visit. Patients will be asked to complete “traditional” and “non-traditional PROs at baseline. The “traditional” PROs will be repeated at recurrence, and at routine intervals post-procedure (e.g., at 3, 6, and 12 months). For patients with Internet access and email connectivity, interval PRO completion may be done directly by the patient into the web-based data capture instrument, with automated email reminders to patients at each PRO interval. For patients without Internet/email access, completion of PROs will be via mailed or in person paper forms, or over the phone with a member of the research team; the research staff will then will transfer PRO data from paper to the EDC.

- Patient Generated Health Data (PGHD). Patient reported health data will be captured, an example of this is home peak flow measurements (obtained with a handheld asthma peak flow monitoring device supplied by the study) or number of steps taken during the week.
- Specimen. Biospecimens collected during routine standard of care from each patient (such as tracheal biopsies obtained during surgery, or surgical specimens generated thru open reconstructive surgeries), will be annotated in the EDC system with a minimum dataset to include date of specimen collection, specimen type (e.g., frozen biopsy tissue; FFPE block), and storage location. Additionally if blood is collected during standard of care, we may ask the participants to consent to providing a one-time blood specimen for research. We plan to obtain 30 mL of blood at a time when other medically indicated labs, operative or office-based procedures occur. A member of the research team will be present at the scheduled blood draw to obtain the necessary research blood and transport to a research lab for storage and analysis. We may examine excess tissue obtained at standard of care surgical biopsy for bacterial pathogens, inflammatory molecular markers, and protein alterations. Techniques will include immunohistochemistry, DNA isolation, PCR, Microarray. We will analyze blood samples for functional immunologic assays, Elispot for IFN-gamma secretion in response to peptide stimulation, flow cytometry for cellular subset abundance, and molecular studies for evidence of t-cell exhaustion and single nucleotide polymorphisms.

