**The secondary objective:** differential treatment quality of life trade-offs will be prospectively and systematically assessed using both validated “traditional” and “non-traditional” patient reported outcome measures (PRO). 4 “Traditional” PRO will measure disability related to voice (VHI-10^1), swallowing (EAT-10^2), breathing (COPD dyspnea), and global quality of life (SF-12) (IR4). 4 “Non-traditional” PROs focused on 1) social support, participatory decision-making style, disease anxiety and burden and fear of disease recurrence will also be administered at the initial visit. Responses to PROs tend to change in chronic disease states since severity of the measured concept is time-variable. This is particularly true for iSGS patients whose symptoms markedly improve after treatment and revert and worsen before subsequent treatments. To better understand the breadth of patient experience with this condition, PROs will employed at a priori determined intervals after diagnosis and treatment, (e.g. immediately pre-intervention, 3, 6, and 12, post-intervention), to obtain a more accurate portrait of the survivorship experience related to the different therapeutic modalities.

**Data analysis plan for secondary endpoints:** The secondary objective of this study is to evaluate the quality of life (QOL) scores, e.g., SF12, Dyspnea index, EAT-10, and VHI10, among three study groups. The 95% confidence interval (CI) method based on the Normal distribution will be applied to estimate the quality of life score among three study groups. The mixed effect model will be applied to exam the correlation between the quality of life score and the study groups.

The strategy to be used for developing the multivariable models for QOL involves the following steps: (1) Apply multiple imputation for missing covariate values to make good use of partial information. (2) Choose an appropriate statistical model based on the nature of the response variable.

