(3) Decide on the allowable complexity of the model (i.e., the number of covariates) based on the effective sample size available. (4) Allow for nonlinear predictor effects using regression splines. (5) Incorporate pre-specified interactions. (6) Check distributional assumptions. (7) Adjust the variance-covariance matrix for multiple imputation. (8) Quantify the clinical utility (discrimination ability) of the model. (9) Internally validate the calibration and discrimination of the model using the bootstrap approach, e.g., .632+ bootstrap, to estimate the model's likely performance on a new set of subjects. The statistical analyses will be completed by either R 3.1.1 or SAS 9.4 statistical program in this project

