**Strategy to address heterogeneity of treatment effect:** Subgroup analysis is the most commonly used analytic approach for examining HTE, and we will utilize an exploratory variant of this analysis in our approach. Definition of subgroups, endpoints, hypotheses, and modeling parameters will be derived in response to the data. An example of this would be the use of a backward model selection approach to identify treatment by covariate interactions. Some of the important types of subgroup variables will be: (1) demographic variables (e.g., age); (2) pathophysiologic variables (e.g., timing after recurrence, disease grade); (3) comorbidities (e.g., presence of diabetes); and (4) concomitant exposures (e.g., hormone replacement therapy, proton pump inhibitors). Additionally, “non-traditional” characteristics that affect patient decision-making (e.g. social support, patient decision-making style, disease related anxiety, baseline quality of life) will be collected to improve risk-adjustment and increase the individualization of the results. Although it is extremely difficult to obtain the sampling properties of subgroup effect estimators (e.g., standard errors), post hoc exploratory subgroup analyses may identify promising hypotheses that will be subject to more rigorous future examination.

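### Aim III names no PRO occasions, baseline role or visit clock for its mixed model; if all collected scores are fitted by group alone, recurrence-triggered records tilt cycling measures against the group that recurs more

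*Combined protocol and SAP*

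**What the plan says.** **Collection (section 5.0, data collection).** Patients complete the traditional instruments (VHI-10, EAT-10, COPD dyspnea, SF-12) and the "non-traditional PROs at baseline". The traditional "PROs will be repeated at recurrence, and at routine intervals post-procedure (e.g., at 3, 6, and 12 months". On the recurrence form: "At patient recurrence, information regarding the date of recurrence will be captured as for the initial procedure".

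**Schedule in the statistical section (12.0, secondary objective).** "PROs will employed at a priori determined intervals after diagnosis and treatment, (e.g. immediately pre-intervention, 3, 6, and 12, post-intervention". This list is given as an example and does not name recurrence.

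**Model (12.0, secondary endpoints).** "The mixed effect model will be applied to exam the correlation between the quality of life score and the study groups". The model-building steps that follow allow covariates, regression splines and pre-specified interactions, and include this one: "Decide on the allowable complexity of the model (i.e., the number of covariates) based on the effective sample size available". None of them names a visit, an occasion or time since procedure.

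**Elsewhere in 12.0.** Time relative to recurrence appears only as an exploratory subgroup variable: "pathophysiologic variables (e.g., timing after recurrence, disease grade". Baseline quality of life (SF-12) is listed for risk adjustment and for the propensity model. Nothing gives a role to the baseline dyspnea, voice or swallowing score. The text also does not say whether the first or every recurrence is scored, or whether the 3/6/12-month clock restarts after a repeat procedure.

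**The concern.** An assessment triggered by recurrence is taken when the patient is near the worst point of the cycle. Section 12.0 describes the cycle: "iSGS patients whose symptoms markedly improve after treatment and revert and worsen before subsequent treatments". Section 1.0 says that dilation recurs more often than the alternatives and that open surgery appears to recur less. The number of worst-state records per patient therefore depends on treatment.

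Scheduled scores already carry the real burden of spending more time symptomatic. Recurrence records added to them, with no term to mark them, count part of that burden again.

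Aim III exists to set breathing, voice, swallowing and global quality of life against each other by treatment. An artefact confined to measures that rise and fall with the stenosis would distort that trade-off, because it would move dyspnea and leave steadier measures alone.

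**Working it through.** **No figure to reproduce.** The documents give no sample size, precision or effect size for the PROs. The half-widths in section 12.0 concern time to recurrence only.

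**Step 1. Direction, in closed form.** Suppose each patient has 3 scheduled scores and *r* recurrence scores, and a recurrence score is *A* worse. The pooled group difference then shifts by

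A × [r_H/(3 + r_H) − r_L/(3 + r_L)].

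The group rates are assumptions, since the documents give none. With r_L = 0.1, the second term is 0.1/3.1 = 0.032.

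| r_H | r_H/(3 + r_H) | Shift |
|---|---|---|
| 0.3 | 0.091 | 0.06 A |
| 0.5 | 0.143 | 0.11 A |
| 0.8 | 0.211 | 0.18 A |
| 1.75 | 0.368 | 0.34 A |

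The top rate is the all-approach median of surgeries per year in section 1.0 (95% CI 0.8 to 2.6), used here as an upper assumption.

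**Step 2. The same in a mixed model, milder assumptions.** Random-intercept REML, 800 v 100 patients, 12 months, intraclass correlation 0.5, total SD 1, visits counted from the index procedure, no true difference at scheduled visits.

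- A = 1 SD, pooled without an occasion term: 0.05, 0.10, 0.16 and 0.30 SD at 0.3, 0.5, 0.8 and 1.75 recurrences/yr v 0.1.
- A = 0.5 SD at 0.5/yr: 0.05 SD.
- With an occasion factor, or scheduled scores only: 0.00 to 0.01 SD.
- If the group that recurs more is truly 0.30 SD better (A = 1 SD, 0.5/yr), pooling shrinks its advantage to 0.20 SD.
- A score that does not cycle: 0.016 SD with or without recurrence records.

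**Step 3. Scores that cycle over the full range.** Assumptions: linear 0-100 sawtooth, gamma (shape 2) cycles, between-patient and residual SD 10, 800 dilation v 100 open, index clock. The 6.9-month cycle is 12/1.75; the 15, 30 and 60 months are assumed. The truth used for reference is the 12-month time-averaged difference. Resection is left out because the documents give no recurrence direction for it.

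| Records in the model | 6.9 v 60 | 15 v 60 | 6.9 v 30 | 15 v 30 |
|---|---|---|---|---|
| Time-averaged truth | 27.2 | 19.4 | 17.8 | 10.0 |
| (a) Scheduled only | 28.8 | 20.8 | 18.7 | 10.5 |
| (b) a + every recurrence | 44.9 | 28.6 | 32.0 | 15.6 |
| (c) a + first recurrence | 39.0 | 27.5 | 26.4 | 14.6 |
| (d) Scheduled + baseline row | 21.6 | 15.6 | 14.0 | 7.9 |
| (e) d + every recurrence | 31.6 | 20.3 | 22.4 | 11.0 |
| (f) d + first recurrence | 27.7 | 19.5 | 18.7 | 10.3 |
| Scheduled, treatment-by-visit, baseline covariate | 28.8 | 20.8 | 18.7 | 10.4 |

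Like for like, the smallest effect of recurrence records is (d) to (f) at 15 v 60: 19.5/15.6 − 1 = 25%. The largest is (a) to (b) at 6.9 v 30: 32.0/18.7 − 1 = 71%. Making baseline an outcome row acts separately and pulls the contrast down: (d) against truth at 6.9 v 60 is 21.6/27.2 − 1 = −21%.

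**Step 4. The clock.** If 3, 6 and 12 months are counted afresh from each procedure, the scheduled scores are themselves selected by recurrence. With a group term only they give 35.6, 22.4, 25.0 and 11.8. Against truth that is +31%, +15%, +40% and +18% (for example 25.0/17.8 − 1 = 40%). A visit term does not repair this: at 6.9 v 60, visit-adjusted scheduled scores gave 46.5, and all scores with an occasion term and baseline covariate gave 45.5, against 27.2 (5 replicates). The standardised model agrees: at 1.75/yr, 0.46 and 0.45 SD against a time average of 0.30. The reason is that, at a fixed time since the last procedure, a patient with short cycles is further through the cycle.

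**The case against.** **The plan does not state a pooled, group-only analysis.** This stands. The one-sentence model is a summary. The text around it calls PRO severity time-variable, lists pre-intervention and 3, 6 and 12 months, and in the missing-data section matches on data from the previous time point. A careful analyst could well add a visit term, but nothing requires it.

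**Recurrence may be covered by the pre-intervention occasion.** Possible: for a repeat procedure the two may be the same assessment. That does not settle whether such a score is an outcome row, so the gap remains.

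**The detail may be in the appendices.** Section 5.0 refers PROs and case report forms to appendices that are not in the public text. They may settle collection timing. The model is described in section 12.0, and the gap there is in intact text.

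**The sizes are assumption-driven.** This stands. An amplitude of 100 is about 7 times the assumed total SD (√(10² + 10²) ≈ 14). In row (f) the pooled estimate is close to the time average, but only because the baseline row and the recurrence row offset each other under a linear shape. With late-rising symptoms (cubed sawtooth) at 6.9 v 60, row (f) gives 22.6 against a truth of 16.0.

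**The plan adopts no time-averaged estimand.** Correct, so errors against truth depend on that choice of reference. The like-for-like increase of 25% to 71% does not.

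**Conclusion.** The point holds as a conditional one. Section 12.0 leaves open which occasions are outcome rows, how baseline scores are used and which clock applies. The literal group-only model, fitted to all collected scores, shifts cycling measures against the group that recurs more. The direction follows from the plan's own statements. The size does not: it is 25% to 71% for recurrence records alone under the full-range sawtooth, and about 0.05 to 0.10 SD under the milder assumptions (A = 1 SD at 0.3 to 0.5 recurrences/yr, or A = 0.5 SD at 0.5/yr, against 0.1/yr).

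A reader might infer more, and the documents do not support it:

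- *That the sponsor will run a biased analysis.* The plan is silent; it does not commit to pooling.
- *That recurrence records double the estimated trade-off.* A ratio near two appears only between rows (b) and (d) (44.9/21.6 = 2.1), which also changes whether baseline is an outcome row.
- *That all four PROs are affected.* Only scores that cycle are. The plan describes cycling symptoms in general, and how far voice, swallowing and SF-12 scores cycle is not given.
- *That an occasion term is enough.* It is enough on an index clock, with baseline as a covariate. On a restarted clock it is not.

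This should be changed, but for a secondary endpoint and with medium confidence in the size.

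**What to change.** In section 12.0, in this order:

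1. For the Aim III contrast, count the 3-, 6- and 12-month visits from the index (first on-study) procedure, with no restart after a repeat procedure. This comes first because the later steps do not remove the bias under a restarted clock.
2. Use each PRO's baseline score as a covariate, not as an outcome row.
3. Compare treatments on the scheduled scores with a treatment-by-visit mixed model.
4. Keep recurrence-triggered scores out of that contrast. Report them separately as scores at recurrence, and say whether the first or every recurrence is included.

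Bring the example schedules in sections 5.0 and 12.0 into line with this. If some sites have timed questionnaires from the latest procedure, say how dated scores are assigned to windows counted from the index procedure.

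The cost is SAP wording and a little more analysis work. The small downside is that recurrence scores do not add to the main contrast. No new data are needed.
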